## 1) **Protocol Title**

Pre vs. postoperative adductor canal block for total knee arthroplasty: prospective randomized trial

## 2) **Objectives\***

The purpose of this project is to determine if a change in patient reported pain, nausea and vomiting after total knee arthroplasty can be observed with the substitution of post operative adductor canal block for a preoperative adductor canal block in the current established peri-operative pain protocol and if these changes lead to a decrease in opioid consumption (in morphine equivalents).

## 3) **Background\***

Levels of postoperative surgical pain are often high, particularly in orthopedic procedures such as total joint replacement [1, 2]. Increases in postoperative pain not only present discomfort to the patient, but can increase length of postoperative hospitalization and affect overall quality of life [3]. Furthermore, increases in postoperative pain have previously been associated with increased use of opioid pain medications which can later lead to addiction [4].

Due to these implications, there has been interest in exploring more effective options in pain management after total joint replacement including various types of multimodal pain management strategies. Currently, guidelines widely suggest that opioid usage should be minimized with a larger focus on options such as multimodal pain management, though the optimal multimodal protocol has yet to be established. [5-6]

Adductor canal blocks have been demonstrated to be effective in reducing post-operative pain, reducing the amount of opioid medication required, thus reducing the adverse effects related to opioids, as well as improving the recovery time required [7-9].

Whether the adductor canal block must be performed preoperatively versus immediately postoperatively, however, has yet to be investigated. While preoperative blocks are effective in reducing the postoperative pain, by performing the adductor canal block immediately postoperatively, the analgesic benefits to the patient will potentially last longer into their postoperative recovery as the administration will be held until the end of the procedure.

## 4) **Inclusion and Exclusion Criteria\***

### Inclusion criteria-

- 1- Patients over the age of 18,
- 2- Patients undergoing primary total knee replacement at the University of Miami Hospital,

### 3- Patients that have capacity to provide medical consent

#### Exclusion criteria-

- 1- All patients under the age of 18
- 2-Prisoners, diabetics, increased risk of bleeding, pregnant women, women planning on becoming pregnant in the next year, and women who think they might be pregnant.
- 3- Patients with prior surgery or history of infection on the joint of interest.
- 4- Patients on steroid preoperatively.
- 5-Inability to provide medical consent.
- 6- Patients with a history of significant unmitigated pain in parts of their body not including the knee the procedure is to be performed or a history of pain catastrophizing (the tendency to magnify the threat value of the pain stimulus and to feel helpless in the context of pain, and by a relative inability to inhibit pain-related thoughts in anticipation of, during or following a painful event) regarding pain anywhere in the body.
- 7-Any condition that, in the opinion of the investigator, would compromise the well-being of the patient or the study or prevent the patient from meeting or performing study requirements will exclude the participant.
- 8-Allergy to local anesthetic or any medication used in the standard protocol for joint replacement.

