**6-Oxycodone 5mg every 4 hours as needed for pain during the first 1-2 weeks postop**

After surgery, patients will be evaluated for the primary outcome of pain status at time points 2 hours and 24 hours using the numeric rating pain scale (0-10). Patient's nausea and vomiting will be evaluated by using a binary "yes" or "no" for nausea and recording the number of episodes of vomiting. The Apfel score will be used during statistical analysis to explore possible causes for differences in nausea and vomiting (0-4). Opioid consumption will also be recorded during the first 24 hours and converted to morphine milliequivalents using patient medical records. Patient data will then be compiled for statistical analysis.

Patients will be assessed routinely once every hour by the circulating nurse for the duration of their care in the hospital. Should a patient receive ambulatory care and depart from the hospital before 24 hours have elapsed, they will be contacted via telephone for assessment using the numeric rating pain scale (1-10) and post-op nausea and vomiting.

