### **Simplified Apfel Score**

Risk Factors	Points
Female Gender	1
Non-Smoker	1
History of PONV	1
Postoperative Opioids	1
Sum =	0 ... 4

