## 8) Study Endpoints\*

- *Primary endpoint – change in pain score at time points 2 hours and 24 hours after primary total knee arthroplasty for each group. The numeric pain rating scale will be used- a higher pain score would indicate higher pain levels. It is scaled from 0-10.*
- *Secondary endpoint - (1) Total opioid consumption in the immediate post-operative period (preoperative block versus postoperative block) (2) change in patient nausea scores and vomiting scores at time points 2 hours, and 24 hours (3) duration of hospital stay.*

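### Preoperative opioid use is neither an eligibility criterion nor a recorded baseline variable, so the unadjusted comparison of 24-hour opioid consumption gives up some precision and hides any chance imbalance

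*Combined protocol and SAP*

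**What the plan says.** **Eligibility (section 4).** One exclusion names a preoperative medicine: "4- Patients on steroid preoperatively". Two others come near the subject without setting an opioid rule. Exclusion 6 covers "Patients with a history of significant unmitigated pain in parts of their body not including the knee the procedure is to be performed", together with pain catastrophizing. Exclusion 7 is discretionary: "7-Any condition that, in the opinion of the investigator, would compromise the well-being of the patient or the study". No criterion names opioids.

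**Outcome.** Section 2 asks, alongside pain, nausea and vomiting, "if these changes lead to a decrease in opioid consumption (in morphine equivalents". Section 8 makes pain the primary endpoint and lists as the first secondary endpoint "Total opioid consumption in the immediate post-operative period (preoperative block versus postoperative block".

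**Recording.** Section 5 states: "Opioid consumption will also be recorded during the first 24 hours and converted to morphine milliequivalents using patient medical records". The only other opioid item is in the simplified Apfel score, "Postoperative Opioids". It also refers to the period after surgery, and the score is meant for exploring nausea and vomiting.

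**Analysis.** Section 9 compares morphine equivalents between arms by t test or Mann-Whitney U test with confidence intervals and names no covariate. Sections 5 and 7 describe 1:1 allocation and name no stratification factor. Section 7 speaks of matching but gives no matching variable.

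**The concern.** A patient who takes opioids only for the knee being replaced meets every listed criterion unless an investigator invokes exclusion 7. What such a patient takes in the first 24 hours reflects usual requirement as well as block timing, and the planned data cannot separate the two.

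The stake is modest. A mixture of users and non-users widens the spread of the opioid outcome, so the two-sample comparison is less sensitive than it could be. With 42 per arm, users may also fall unevenly by chance. Without a baseline field, neither the team nor a reader could see whether that had happened. For nausea and vomiting the plan does provide an explanatory risk score. For opioid consumption it provides nothing comparable.

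**Working it through.** **1. The plan's own figure.** The only sample size is for pain (section 7): SD 3, difference 2, alpha 0.05 (taken as two-sided), power 0.80. The normal formula gives 2 × [3 × (1.960 + 0.842) / 2]² = 35.3, which rounds up to 36 against the stated 35. Power at 35 is 79.6%, so the figure reproduces within rounding. No size or power is stated for opioid consumption. I use 35 per group below only as the plan's own reference.

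**2. Inputs that the documents do not give.** Let p be the share of preoperative users. Let D be their extra 24-hour consumption, in units of the SD among patients of the same user status within an arm. Both are assumptions: p = 10% to 20%, D = 0.5 to 1.

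**3. Variance and power.** Leaving user status out multiplies the variance by v = 1 + p(1 − p)D². Take the effect that has 80% power at 35 per group when status is adjusted for: 2.802 × √(2/35) = 0.67 SD. Unadjusted power is then Φ(2.802/√v − 1.960), and the n per group that restores 80% is 35v, rounded up.

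| p | D | v | Unadjusted power | n per group for 80% |
|---|---|---|---|---|
| 10% | 0.5 | 1.02 | 79% | 36 |
| 20% | 0.5 | 1.04 | 78% | 37 |
| 10% | 1 | 1.09 | 77% | 39 |
| 20% | 1 | 1.16 | 74% | 41 |

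**4. Chance imbalance.** With 42 per arm, the SD of the between-arm difference in number of users is √(84p(1 − p)): 2.75 at p = 10% and 3.67 at p = 20%. From two independent binomial counts, the probability that the arms differ by at least 10 percentage points is 10% and 22% respectively. A 10-point imbalance shifts the unadjusted difference by 0.1 × D, that is 0.05 to 0.10 SD, against the 0.67 SD effect in step 3.

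**5. Check against the listed oxycodone order.** Section 5 lists 5 mg every 4 hours as needed. That is 24/4 = 6 doses, or 30 mg in 24 hours, and 45 morphine milligram equivalents (MME) at an assumed conversion of 1.5. A variable confined to 0 to 45 cannot have an SD above 45/2 = 22.5. Now suppose an SD of 20 MME within user status and users taking 40 to 80 MME more:

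- p = 10%, +40: √(400 + 0.09 × 1,600) = 23.3
- p = 20%, +40: √(400 + 0.16 × 1,600) = 25.6
- p = 10%, +80: √(400 + 0.09 × 6,400) = 31.2
- p = 20%, +80: √(400 + 0.16 × 6,400) = 37.7

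All four exceed 22.5. With seven doses the limits are 52.5 MME and 26.3, and the last two remain out of reach. Excesses of that size need opioid beyond the listed order.

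**The case against.** The strongest reply is that nothing here is invalid. Allocation is random, so the unadjusted comparison is unbiased, and chance imbalance in users is part of the sampling error that alpha and the confidence interval already cover. The outcome is secondary, and the plan claims no power for it. Every input to the size is assumed, and at the low end (v = 1.02) the loss is negligible. All of this stands, and it is why the point is about precision and a baseline check only.

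A second reply is that the plan may use the Mann-Whitney test, which is less sensitive to a spread-out tail. That matters for large excesses but not in the range used here. At p = 20% and D = 1 with normal components, the relative efficiency is (0.68 + 0.32e^−0.25)² = 0.86. The t test gives 1/1.16 = 0.86.

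A third reply is that opioid totals already come from medical records, so preoperative use could probably be retrieved later. That is fair: the gap is in prespecification, not irretrievable data. But a covariate chosen after the results are known carries less weight than one named beforehand.

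Finally, keeping opioid users is a legitimate pragmatic choice. That also stands.

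**Conclusion.** The point holds as a limited one. Patients taking opioids for the index knee are eligible, their preoperative use is not a planned data item, and a secondary outcome named in the objective is compared without allowing for it. With 10% to 20% users taking 0.5 to 1 within-group SD more, variance rises by about 2% to 16%, and power falls from 80% to about 79% to 74% at 35 per group. These are assumption ranges, because the documents give neither a prevalence nor an opioid SD.

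A reader might infer more than the documents support:

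- **Systematic bias in the block comparison.** Randomisation rules this out.
- **A large loss.** At p = 40% and D = 2, v would be 1.96 and power 52%, but nothing in the documents points to such values. Large excesses in MME would need opioid outside the oxycodone order, such as PACU or continued home opioids. PACU orders are not itemised, and the plan does not say whether home opioids count. The cap is in MME, so a small within-group SD would still allow a larger D.
- **A flaw in the primary endpoint.** Preoperative use may also add noise to pain scores, but the documents allow no figure for that. The planning SD of 3 comes from an outside trial whose eligibility is not shown.
- **An inconsistent aim behind the exclusions.** Section 4 gives no reason for excluding steroid users, so that line does not show an intent that opioid users defeat.

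**What to change.** In section 5, add preoperative opioid use (yes/no and daily morphine equivalents), taken from the chart before randomisation, and report it by arm. In section 9, prespecify it as a covariate for opioid consumption and for the pain scores: a linear model, or a rank test stratified by yes/no use if the data are non-normal. State in advance which form of the variable enters the model. With 8 to 17 users among 84 under the assumptions above (84 × 0.1 = 8.4; 84 × 0.2 = 16.8), the yes/no form spends one degree of freedom.

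The cost is one extra chart field and a slightly more complex analysis in place of the plain two-sample test. Excluding opioid users is not part of this fix: it would trade recruitment and generalisability for a more uniform sample, and that choice is the sponsor's.

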## 5) Procedures Involved\*

Study design: All patients who fulfill inclusion criteria, including undergoing a pregnancy test if a woman of childbearing age, undergoing total knee arthroplasty will be randomized to one of two groups to be given the standard orthopaedic joint replacement protocol including general anesthesia with the preoperative adductor canal block **or** the standard orthopaedic joint replacement protocol including general anesthesia except the adductor canal block will be given at the end of the procedure instead of the beginning. General anesthesia for the groups will be standardized, and no intraoperative analgesics given. Nerve blocks will be placed for both groups by anesthesiologists as is the standard protocol. All nerve blocks will be placed following the same procedural protocol with the same supplies under ultrasound guidance to ensure consistency and minimize variation. Nerve blocks in both groups will include the standard 20mL Ropivacaine 0.2% (local anesthetic) injected in the same manner. PACU orders will not differ between the groups and will be the standard procedure for total joint arthroplasty at the facility. Cases will be assigned randomly in a 1:1 fashion. A computer program such as Microsoft Excel will be employed for the randomization process.

***Standard orthopaedic joint replacement protocol at our institution includes all of the following:***

- 1. Dexamethasone 10mg IV once postoperatively within 24 hours for pain and swelling**
- 2- Tylenol 1,000mg every 8 hours for pain during the first 1-2 weeks postop**
- 3- Lyrica 75mg nightly for pain during the first 1-2 weeks postop**
- 4- Celebrex 200mg twice a day for pain and swelling during the first 1-2 weeks postop**
- 5-Meloxicam 30mg IV once postoperatively within 24 hours for pain and swelling**

[figure not shown]
**6-Oxycodone 5mg every 4 hours as needed for pain during the first 1-2 weeks postop**

After surgery, patients will be evaluated for the primary outcome of pain status at time points 2 hours and 24 hours using the numeric rating pain scale (0-10). Patient's nausea and vomiting will be evaluated by using a binary "yes" or "no" for nausea and recording the number of episodes of vomiting. The Apfel score will be used during statistical analysis to explore possible causes for differences in nausea and vomiting (0-4). Opioid consumption will also be recorded during the first 24 hours and converted to morphine milliequivalents using patient medical records. Patient data will then be compiled for statistical analysis.

Patients will be assessed routinely once every hour by the circulating nurse for the duration of their care in the hospital. Should a patient receive ambulatory care and depart from the hospital before 24 hours have elapsed, they will be contacted via telephone for assessment using the numeric rating pain scale (1-10) and post-op nausea and vomiting.

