## **10) Risks/Benefits**

This study is a prospective cohort study that will collect private, identifiable information about human subjects. The main risk is to subjects' confidentiality should an individual outside of the study team access the study data.

There may be no direct benefit to subjects.

The group receiving the postoperative nerve block may have better pain control and less opioid use.

This research might lead to the benefit of others should the analysis of the data lead to better selection of surgical candidates and possible interventions to reduce adverse outcomes.

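### The four-item Apfel total mixes three baseline risk factors with postoperative opioid use, which block timing may change, so as an exploratory explanation of nausea and vomiting it can absorb part of a block effect

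*Combined protocol and SAP*

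**What the plan says.** Section 5 (Procedures Involved) gives the score one job: "The Apfel score will be used during statistical analysis to explore possible causes for differences in nausea and vomiting (0-4".

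The Simplified Apfel Score table awards one point each for "Female Gender", non-smoking, "History of PONV" and "Postoperative Opioids", summed to a total of 0 to 4.

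Section 8 (Study Endpoints) lists as secondary endpoints both "Total opioid consumption in the immediate post-operative period (preoperative block versus postoperative block" and "change in patient nausea scores and vomiting scores at time points 2 hours, and 24 hours".

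Two places show that the plan expects block timing to act on opioid use. Section 2 (Objectives) asks "if these changes lead to a decrease in opioid consumption (in morphine equivalents", and Section 10 (Risks/Benefits) says: "The group receiving the postoperative nerve block may have better pain control and less opioid use".

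Oxycodone is given as needed under the standard protocol in Section 5. Intake over the first 24 hours is recorded and converted to morphine equivalents.

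Section 9 (Data Management) compares nausea and vomiting between arms by t test or Mann-Whitney U. It does not mention the Apfel score. Nothing in the document says whether the opioid item is scored as planned or as received, or in what form the score enters an analysis.

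**The concern.** Sex, smoking status and history of PONV cannot be changed by the block. Postoperative opioid use can, and lower opioid use is a plausible route by which block timing would reduce nausea and vomiting. Adding the four points together puts that route in the same number as baseline risk. A total of 2 may mean two baseline factors, or one baseline factor plus opioid use.

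Suppose the arms differ in nausea and the investigators turn to the total for an explanation. The arm with fewer opioid users will have a lower mean score because of the treatment. Adjusting for or stratifying on the total then removes part of the treatment effect, and the difference could be written up as one of patient risk when the block produced it.

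**Working it through.** No figure in the plan bears on this point, so there is none to reproduce. The check has two parts.

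**1. Timing of the items**

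| Item | Fixed before randomisation? | Can block timing change it? |
|---|---|---|
| Female sex | Yes | No |
| Non-smoker | Yes | No |
| History of PONV | Yes | No |
| Postoperative opioids | No | Yes if scored as received; no if scored as planned |

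One of the four points is therefore a possible consequence of treatment. Scored as planned, every patient earns it, because as-needed oxycodone belongs to the standard protocol for both arms. The item is then constant: it does no harm and adds no information.

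**2. Size, if scored as received and used for adjustment**

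The documents give no opioid-receipt or nausea rates, so every input here is an assumption:
- Nausea risk rises by βo = 0.20 with any opioid and by βb = 0.10 per baseline item.
- The block acts only through opioid receipt.
- The baseline items are independent, with prevalences 0.6, 0.8 and 0.3. Their summed variance is Vb = 0.24 + 0.16 + 0.21 = 0.61.
- Allocation is 1:1.

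Let Δ be the arm difference in opioid receipt, and Vo the average within-arm variance of receipt. In a linear model:
- Total effect = βo × Δ.
- Effect adjusted for the three baseline items = βo × Δ, because randomisation balances those items.
- Effect adjusted for the four-item total = (βo − βb) × Δ × (1 − g), where g = Vo / (Vo + Vb).

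The last line follows from writing risk as a constant + βb × total + (βo − βb) × opioid. The total takes up the first part, and also a share g of the opioid difference.

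*80% versus 50% receipt.* Δ = −0.30. Vo = (0.16 + 0.25)/2 = 0.205. g = 0.205/0.815 = 0.252.
- Total effect: 0.20 × (−0.30) = −6.0 points.
- Adjusted for the four-item total: 0.10 × (−0.30) × 0.748 = −2.2 points (about 63% removed).
- Adjusted for the three baseline items: −6.0 points.
- Mean Apfel totals: 2.50 versus 2.20, a gap of 0.30 that is due to treatment alone.

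*95% versus 90% receipt.* Δ = −0.05. Vo = (0.0475 + 0.09)/2 = 0.06875. g = 0.06875/0.67875 = 0.101.
- Total effect: 0.20 × (−0.05) = −1.0 point.
- Adjusted for the four-item total: 0.10 × (−0.05) × 0.899 = −0.45, or about −0.4 points.

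*Equal receipt.* Δ = 0, so there is no effect through opioids and nothing to distort.

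*Sensitivity to the weights.* Take βb = 0.15 and receipt of 90% versus 70%. Then Vo = (0.09 + 0.21)/2 = 0.15 and g = 0.15/0.76 = 0.197. The total effect is −4.0 points, and the adjusted one is 0.05 × (−0.20) × 0.803 = −0.8 points (about 80% removed). The closer an opioid point and a baseline point are in their effect on nausea, the more is lost.

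**The case against.** The strongest reply is that the harmful analysis is not in the plan. No section makes the score a covariate or stratifier, and none calls it a baseline score. The only tests named for nausea and vomiting, in Section 9, are unadjusted. Exploring possible causes could legitimately include opioids as a cause, and since the items are listed singly and opioid intake is recorded separately, an item-by-item look is already possible.

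Most of this stands and limits the point. A reader might infer that the planned nausea and vomiting comparison is biased; the documents do not support that, because that comparison does not use the score. It remains true that the only stated use of the score is as a 0-4 total to explain arm differences, and that total cannot isolate opioids as a mediator any more than it can isolate baseline risk.

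Three further replies have weight:
- The item records any opioid use, whereas the endpoint is total dose. Block timing could lower the dose while nearly everyone still takes at least one tablet. The item would then be almost constant and the distortion small, as the 95% versus 90% case shows.
- With 42 per arm and an assumed nausea rate of 40%, the standard error of the difference is √(2 × 0.4 × 0.6/42) = 0.107, about 11 points. A shift from −6 to −2 would be hard to see in this trial.
- A reader might also infer that the 0-4 range is wrong, since scoring by planned use gives 1-4. It is not an error: 0-4 is the range of the instrument as printed in the table, not a claim about the values to be observed.

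**Conclusion.** The point holds in a limited form. Used as Section 5 describes, with the opioid item scored from actual receipt, the Apfel total combines baseline risk with something the plan expects treatment to change. It can therefore absorb part of a block effect that runs through opioids. Scored as planned use, the item is uninformative. The document does not say which scoring applies.

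Under the assumed risks, between about half and four fifths of such an effect is removed in the scenarios shown where receipt differs by arm. In absolute terms the loss is about 3.8 points at 80% versus 50%, about 0.6 at 95% versus 90%, and zero at equal receipt. The direction depends on receipt differing between arms and on the total being used to adjust, stratify or explain. The sizes depend entirely on the assumed inputs.

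It would go too far to say that the trial cannot separate baseline risk from treatment effect. That limit belongs to the summed score; the items taken separately can do it. The consequence is confined to the exploratory interpretation of a secondary endpoint. The primary pain analysis, the opioid comparison and the unadjusted nausea and vomiting tests are unaffected. This is a cheap improvement, not a threat to the trial's main conclusions.

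**What to change.** In Section 5, replace the sentence on the Apfel score with two statements:
- The exploratory nausea and vomiting analysis uses a baseline risk score of the three pre-randomisation items (sex, smoking status, history of PONV; range 0-3).
- Opioid intake is examined separately as a post-randomisation variable, using the 24-hour morphine-equivalent total already recorded.

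The four-item total (0-4, as in the Apfel table) can still be reported descriptively, with a statement of whether its opioid item is scored as planned or as received. The table itself then needs no change. Making the edit before unblinding also avoids choosing the scoring after seeing the data.

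The cost is a change of wording; no new data are needed. The one drawback is that the score used in the analysis is no longer the standard four-item total.

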## **6) Study Timelines\***

- *Participants will be active in the study for the 24 hours after the index knee replacement surgery.*
- *It will take about 6 months from the start of the study to recruit the total anticipated participants.*
- *We will allot 1 month after the final participant has completed the study for analysis and write up.*

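### No source is stated for opioid doses taken at home before hour 24, so the 24-hour opioid total may be undercounted for patients discharged early

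*Combined protocol and SAP*

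**What the plan says.** Section 5 (Procedures Involved) describes the opioid outcome in one sentence: "Opioid consumption will also be recorded during the first 24 hours and converted to morphine milliequivalents using patient medical records".

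The same section lists, as part of the standard regimen for both groups, "Oxycodone 5mg every 4 hours as needed for pain during the first 1-2 weeks postop". The permitted use therefore extends well past hospital discharge.

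Section 5 then provides for patients who go home early. Its condition is "Should a patient receive ambulatory care and depart from the hospital before 24 hours have elapsed", and what follows is that "they will be contacted via telephone for assessment using the numeric rating pain scale (1-10) and post-op nausea and vomiting". The hourly nurse assessments in that paragraph apply only while the patient is in hospital.

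Section 6 (Study Timelines) fixes the participation period: "Participants will be active in the study for the 24 hours after the index knee replacement surgery". Section 8 (Study Endpoints) makes opioid use secondary endpoint (1), worded as "Total opioid consumption in the immediate post-operative period", and also lists duration of hospital stay. Section 9 (Data Management) compares morphine equivalents between groups by a t test or Mann-Whitney U test. It gives no rule for incomplete opioid totals.

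**The concern.** The outcome window is 24 hours, but for some patients the hospital's observation may end sooner. The plan noticed this for pain and for nausea and vomiting, and extended follow-up by telephone to cover them. It did not do the same for opioid use. An early leaver who takes oxycodone at home before hour 24 has doses inside the stated window with no stated way of reaching the data set. The plan does not say whether such doses count as zero, are missing, or fall outside the endpoint.

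Reduced opioid use is part of the trial's stated objective (section 2) as well as a secondary endpoint, so an incomplete total bears on one of the conclusions the trial is meant to support. If home doses are missed to a similar degree in both arms, a true difference can be diluted. If the arms differ in how many patients leave early, or in how much those patients take at home, the comparison can be biased. Home doses cannot be recovered reliably after the event, so the rule has to be set while they can still be asked about.

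**Working it through.** **Is there a source anywhere?** The sections compare as follows.

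| Section | What it covers | Source for home opioid doses |
|---|---|---|
| 5, opioid sentence | First 24 hours | Mentions medical records only |
| 5, nurse assessments | Hospital stay | None after discharge |
| 5, telephone contact | Pain, nausea and vomiting | Not listed |
| 6, timelines | 24 hours of participation | None |
| 8, endpoints | Opioid total, window worded more loosely | None |
| 9, analysis | Morphine equivalents | None |
| 11, adverse events | 24 hours | None |

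No diary, pill count, patient report or missing-data rule for opioids appears. A discharge prescription in the records would show what was supplied; nothing says the records show what was taken.

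**Ceiling per patient.** The plan states no figure for the opioid endpoint, so there is none to reproduce. The sample size in section 7 concerns the pain score and does not bear on this point. Inputs from section 5 are 5 mg per dose, one dose per 4 hours, and a 24-hour window. The discharge hour *h* is an assumption, because the documents do not give one.

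- Doses the schedule allows in 24 hours: 24 / 4 = 6, that is 6 × 5 = 30 mg oxycodone.
- Doses it allows from discharge to hour 24: (24 − *h*) / 4.

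| Assumed *h* | Doses without a stated source | Oxycodone | Share of the 6-dose maximum |
|---|---|---|---|
| 4 | (24 − 4) / 4 = 5 | 25 mg | 5/6 = 83% |
| 8 | (24 − 8) / 4 = 4 | 20 mg | 4/6 = 67% |
| 12 | (24 − 12) / 4 = 3 | 15 mg | 3/6 = 50% |

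These are upper limits for a patient who takes every permitted dose. The lower limit is zero. The shares refer to the oxycodone schedule only, not to total morphine equivalents.

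**Effect on the comparison.** Let *p* be the fraction of an arm leaving early and *m* the mean opioid amount an early leaver takes at home before hour 24, in morphine equivalents. If none of it is recorded, that arm's mean is too low by *p* × *m*. With D the true difference between arms A and B,

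recorded difference = D − (p_A × m_A − p_B × m_B).

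- If nobody leaves early, or nobody takes opioid at home, the recorded difference equals D.
- If *p* is equal in both arms, it is D − *p* × (m_A − m_B). The part of the true difference that arises at home among early leavers is lost.
- If *p* differs by arm, the error depends on both *p* and *m*. An arm with more early leavers but lower home use per leaver could have a larger, equal or smaller loss than the other.

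The documents give neither *p* nor *m* for either arm, so neither size nor direction can be calculated.

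**The case against.** The strongest reply is that the text is less exclusive than it may look. The reference to medical records could attach only to the conversion into morphine equivalents, which leaves the commitment to record 24 hours of use unqualified. The telephone list may also not be exhaustive: section 11 has adverse events recorded for 24 hours, yet they are not on that list either. And section 9 speaks of morphine equivalents received, which could mean given in hospital.

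This stands to a point. A reader might infer that medical records are declared the only source and that the endpoint is certainly undercounted. The documents support neither. They do support that no source is stated for home doses: if the records phrase covers only the conversion, no source for the recording is named at all. If only hospital doses are meant, the 24-hour window does not describe the endpoint for early leavers, and the plan should say so.

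A second temptation is to predict the direction. Section 3 says that increased pain "can increase length of postoperative hospitalization and affect overall quality of life", so one might infer that the arm with less pain leaves sooner, loses more doses from the record and shows an exaggerated saving. But that arm would probably also take fewer as-needed doses at home, and ambulatory care may be a planned pathway rather than a response to pain. Nothing in the plan says that block timing changes who leaves before hour 24.

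A third is to read the 83, 67 and 50% as shares of the endpoint. The endpoint is total opioid use. Section 5 refers to standard recovery-room orders without giving their content, and any opioid given there would be in the hospital record.

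**Conclusion.** The point holds as a gap in data capture. For patients discharged before hour 24, the plan states no source for opioid doses taken at home within the outcome window, and secondary endpoint (1) may be undercounted for them if the plan is followed as written.

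The size is unknown and may be zero. The ceiling is 5, 4 or 3 of 6 scheduled oxycodone doses per early leaver. It rests on assumed departure at 4, 8 or 12 hours, on the printed schedule, and on every permitted dose being taken. Dilution of a true difference and bias between arms are both possible; the documents do not allow a choice between them or a statement of direction. The primary pain analysis does not depend on this. The change is worth making because opioid reduction is a named objective and the remedy is small.

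**What to change.** 1. State in section 5 that the telephone call is made at hour 24, and add a question: which opioid, what strength and how many doses were taken since discharge.
2. Define 24-hour morphine equivalents once, as the inpatient record plus reported home doses, and use that definition and window in sections 5, 8 and 9. Treat the home part as missing, not zero, when the call is not completed. State in section 9 how such totals are analysed so that early leavers are not simply dropped.
3. Report by arm the number leaving before 24 hours and their discharge hour, so that readers can judge how far the gap could matter.

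The cost is one question in a call already planned, some wording, and a tabulation of discharge times that the duration-of-stay endpoint already requires. If enrolment has begun, the question can still be added for the remaining patients.

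The downside is that home doses are self-reported while inpatient doses come from the record. If early discharge differs by arm, the mix of measurement sources differs too. Flagging the source of each component and reporting item 3 keeps this visible.
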